4.4.2 Secondary Efficacy Variables

Secondary efficacy variables are defined in [Section 4.5](#)

4.4.3 Handling of Missing Values/Dropouts/Discontinuations

Subjects who withdraw from the study early will be included in the study analysis up to the point of withdrawal. Subjects who withdraw will not be replaced. No data will be imputed in the case of dropouts or missing data.

4.5 Analysis of Secondary Objectives

4.5.1 Efficacy (Secondary)

4.5.1.1 Secondary Efficacy Variable 1

4.5.1.1.1 Secondary Efficacy Endpoint 1 Definition

The first Secondary Efficacy Variable is change from Baseline in Schiff sensitivity score at Day 56. Change from Baseline will be derived for the individual teeth first before calculating the average change for the two test teeth.

4.5.1.1.2 Statistical Hypothesis, Model and Method of Analysis

Study product differences will be tested under the null hypothesis:

- H_0 : there is no treatment difference versus the alternate hypothesis;
- H_1 : there is a treatment difference

Change in Schiff sensitivity score will be analysed at Day 56 using an Analysis of Covariance (ANCOVA)model which will include study product as a factor and Baseline Schiff sensitivity score as a covariate. Note that since the Baseline Schiff sensitivity score will be included as a covariate, the Baseline Schiff stratification value will not be included in the model.

Using the above model, adjusted mean change from Baseline, along with 95% confidence intervals (CIs) will be reported by study product group. P-values testing for non-zero change from Baseline will be presented for both study product groups. Mean difference between study product groups, 95% CIs and p-values will be provided for Schiff sensitivity score in [Table 14.2.2.4.1](#). Significance testing will be conducted at the two-sided 5% significance level; no adjustment for multiple comparisons will be made.

The assumption of normality and homogeneity of variance in the ANCOVA model will be investigated, and if violated, an appropriate data transformation or non-parametric method, for example, the van Elteren test, adjusting for the maximum baseline Schiff Sensitivity scores, will be performed.

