DH is an episodic condition; symptoms are known to vary spontaneously ([West 2008](#), [West et al. 2013](#)). Baseline clinical values that would support enrolment may represent *random highs* in the condition that will be followed by regression to the mean, leaving the subject or a particular sensitive tooth without the condition under investigation during the treatment period. To help minimize the potential for this to occur on the current study, subjects will be required to demonstrate consistency in response at both the Screening and the Baseline visits (qualifying responses to tactile and evaporative air stimuli must be met at Screening and Baseline).

With the growing acknowledgment of the value of information gleaned directly from the subject, self-reported outcome measures have become increasingly important barometers of the benefit of medical interventions. The dentine hypersensitivity questionnaire (DHEQ) is a validated, condition specific measure of impacts on everyday life for DH sufferers which has been shown to have good psychometric properties in both the general population and in a clinical sample of DH sufferers ([Baker et al. 2014](#), [Boiko et al. 2010](#)). A short form of the DHEQ has also been developed and validated ([Machuca et al. 2014](#)), and will be included in this study to evaluate treatment impacts in a clinically diagnosed DH population.

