9.2.4 Selection of Test Teeth

On completion of the Baseline clinical assessments, the clinical examiner will select two ‘test teeth’ for each eligible subject, to be evaluated at all subsequent visits. Test teeth will exhibit none of the dentition exclusions and meet all the inclusion criteria for eligible teeth (including Screening and Baseline tactile threshold \leq 20 g; Screening and Baseline Schiff sensitivity score \geq 2).

Test teeth should not be adjacent to each other and preferably in different quadrants.

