3.1 Baseline Definition

For all endpoints, the baseline value will be the Day 0 (Visit 2) pre-treatment assessment with a non-missing value.

Unless otherwise stated, if baseline data is missing no derivation will be performed and will be set to missing.

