4.4.1.2 Statistical Hypothesis, Model and Method of Analysis

No formal efficacy analysis is planned for primary endpoint.

Summary statistics (mean, median, standard error (SE), SD, minimum, maximum) will be presented for each outcome variable at each assessment time point in [Table 14.2.2.1.1](#), [Table 14.2.2.2.1](#) and [Table 14.2.2.3.1](#) for Schiff sensitivity score, tactile threshold (g) and the number of sensitive teeth respectively. Raw means (\pm SE) of the Schiff sensitivity score, tactile threshold (g) and number of sensitive teeth at each time point will be plotted by study product group in [Figure 14.2.1](#), [Figure 14.2.2](#) and [Figure 14.2.3](#) respectively.

Schiff sensitivity score and tactile threshold (g) for the two test teeth will be listed for each subject by Visit in [Listing 16.2.6.1](#) and [Listing 16.2.6.2](#) respectively. All Schiff sensitivity scores and tactile threshold (g) values recorded throughout the study will be listed by subject in [Listing 16.2.6.4](#) and [Listing 16.2.6.5](#) respectively. The number of sensitive teeth will be listed by subject in [Listing 16.2.6.3](#).

An InForm database outage occurred on 28 May 2019 that prevented the direct entry of source data from twelve (12) subjects into the InForm eCRF database. Subjects [PPD](#) [qualifying oral data \(Oral Soft Tissue \(OST\) Examination, Qualifying Tactile Sensitivity Assessment \(Tactile Threshold\) and Qualifying Evaporative Air Sensitivity Assessment \(Schiff sensitivity score\) were recorded manually on the back of the paper "Subject Source / Medical Record" document. The entries were not signed and dated. Due to this data integrity issue a sensitivity analysis will be performed to compare the results by excluding these subjects to make an inference about the study.](#)

Baseline summary statistics will be repeated for all three primary endpoints ([Table 14.2.2.1.1.1](#) for Schiff sensitivity score, [Table 14.2.2.1.1](#) for tactile threshold (g) and [Table 14.2.2.3.1.1](#) for the number of sensitive teeth) based on mITT population but excluding these 12 subjects and with only with these 12 subjects Supportive Analyses

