4.5.1.2.2 Statistical Hypothesis, Model and Method of Analysis

Study product differences will be tested under the null hypothesis:

- H_0 : there is no treatment difference versus the alternate hypothesis;
- H_1 : there is a treatment difference

Change in tactile threshold (g) will be analysed at Day 56 using an ANCOVA model with study product and Baseline Schiff stratification included as factors and Baseline tactile threshold included as a covariate.

Using the above model, adjusted mean change from Baseline, along with 95% CIs will be reported by study product group. P-values testing for non-zero change from Baseline will be presented for both study product groups. Mean difference between study product groups, 95% CIs and p-values will be provided for tactile threshold (g) in [Table 14.2.2.5.1](#). Significance testing will be conducted at the two-sided 5% significance level; no adjustment for multiple comparisons will be made.

The assumption of normality and homogeneity of variance in the ANCOVA model will be investigated, and if violated, an appropriate data transformation or non-parametric method, for example, the van Elteren test, adjusting for the maximum baseline Schiff Sensitivity scores, will be performed.

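### The Day 56 Schiff model adjusts only for a three-level Day 0 score; pre-specifying the Screening score of the same two teeth as a second covariate could modestly narrow the interval

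*SAP*

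**What the plan says.** SAP 3.1 fixes baseline at one visit: "the baseline value will be the Day 0 (Visit 2) pre-treatment assessment with a non-missing value". The Day 56 Schiff analysis (SAP 4.5.1.1.2; Protocol 12.2.6) is an ANCOVA "which will include study product as a factor and Baseline Schiff sensitivity score as a covariate", and leaves the randomization stratum out on purpose. The Day 56 tactile ANCOVA (SAP 4.5.1.2.2) is fuller, with "study product and Baseline Schiff stratification included as factors and Baseline tactile threshold included as a covariate".

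Protocol 5.2 requires tactile threshold at or below 20 g and Schiff 2 or more, tooth by tooth, at both Screening and Baseline. Protocol 9.2.4 repeats that test teeth must "meet all the inclusion criteria for eligible teeth" at both visits. Screening values go no further than a listing under SAP 4.4.1.2: "All Schiff sensitivity scores and tactile threshold (g) values recorded throughout the study will be listed by subject".

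On testing, SAP 4.5.1.1.2 states: "Significance testing will be conducted at the two-sided 5% significance level; no adjustment for multiple comparisons will be made". Protocol Section 3 counts a significant Day 56 Schiff difference in favour of Test as a success. No correlation, standard deviation, effect size or target interval width is given in either document.

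**The concern.** Protocol 4.2 says that "DH is an episodic condition; symptoms are known to vary spontaneously", and warns that a qualifying value may be a chance high that later regresses to the mean. A single Day 0 reading on a scale cut to two categories per tooth is then a coarse measure of a subject's stable severity. A second reading of the same teeth on another day can help separate stable severity from day-to-day fluctuation. The plan uses the Screening reading to select subjects and then drops it from the estimate.

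What is at stake is precision in the Day 56 Schiff comparison. That matters here because no power calculation supports the sample size, and the trial's stated purpose is to give reliable estimates for designing later studies.

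**Working it through.** **Plan's own figure.** SAP 1.4 wants about 50 evaluable subjects per arm and allows about 4% dropout: 2 × 50 / 0.96 = 104.2, against the stated 104. Conversely 52 × 0.96 = 49.9 per arm. The figure reproduces, so N = 100 is used below.

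**Values the covariate can take.** The Schiff scale ends at 3 (Protocol 9.1.5) and entry requires at least 2, so each tooth scores 2 or 3 and the two-tooth average is 2, 2.5 or 3. The Screening average is limited to the same three values. Any gain comes from a second occasion, not from a finer scale.

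**Effect of one more covariate.** Let r be the partial correlation of the Screening average with the Day 56 change, given treatment and the Day 0 score. With q covariates, the expected variance of the adjusted difference is inflated by 1 + q/(N − q − 3) for chance imbalance. Going from q = 1 to q = 2 at N = 100:

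width ratio = √(1 − r²) × [t(0.975; 96) / t(0.975; 97)] × √[(1 + 2/95) / (1 + 1/96)] = √(1 − r²) × 1.0054

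Equivalent N is 100/(1 − r²).

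| Assumed r | CI width ratio | Equivalent N |
|---|---|---|
| 0 | 1.005 | 100 |
| 0.10 | 1.000 | 101 |
| 0.20 | 0.985 | 104 |
| 0.30 | 0.959 | 110 |
| 0.40 | 0.921 | 119 |

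Break-even is at r of about 0.10. For scale, with an assumed residual SD of 0.6, the planned half-width is 1.985 × 0.6 × √(2/50) = 0.238 Schiff units. It becomes 0.235 at r = 0.2 and 0.228 at r = 0.3.

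**Which r is plausible.** The documents do not say, so r is bracketed by assumption.

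- *Equal correlation.* If Screening, Day 0 and Day 56 have the same pairwise correlation ρ, then r = (ρ − ρ²)/(1 − ρ²) = ρ/(1 + ρ). At ρ = 0.1, 0.2, 0.3 and 0.5, r is 0.091, 0.167, 0.231 and 0.333, and the width ratio is 1.001, 0.991, 0.978 and 0.948.
- *Latent score, Schiff entry rule at both visits, same shift for everyone.* With subject plus tooth variance shares totalling 0.3 to 0.8, r is 0.18 to 0.39 and intervals are 1% to 7% narrower.
- *Latent score, Schiff and tactile entry rules, response SD 0 to 0.8.* Residual variance falls by 1.2% to 11.5%. The width ratio is √0.988 × 1.0054 = 0.999 to √0.885 × 1.0054 = 0.946.
- *A further simulation with entry selection.* This gave r of 0.07 to 0.34, with intervals about 0% to 5% narrower, and only 0% to 1% narrower when response varies between subjects.

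**Cost of a missing Screening value.** A complete-case model with 97 instead of 100 subjects is wider by √(100/97) = 1.015. At r = 0.2, 0.985 × 1.015 = 1.000, so three missing values would cancel the gain.

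**The case against.** The strongest reply is that ANCOVA on the Day 0 score is a standard and valid analysis in an exploratory study whose primary analysis is descriptive, so further covariates are a matter of preference. Several specific points support it.

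- **Screening is not a plain repeat of Day 0.** It precedes the acclimatization phase, and the pre-visit limits on oral hygiene, food and drink in Protocol 5.5.1 and 5.5.2 start at Baseline. Screening may predict Day 56 less well than Day 0 does. This stands, and it pulls r down.
- **Completeness holds only for subjects randomized per protocol.** The mITT definition has no eligibility condition. Under Protocol 9.1.4 a tooth that fails the tactile limit is not tested further. SAP 4.4.3 imputes nothing, so a missing Screening value would remove the subject from the model. This stands.
- **Twelve subjects have unsigned, manually recorded qualifying readings from 28 May 2019** (SAP 4.4.1.2). The SAP does not say which visit these belong to. Any such reading precedes randomization, so using it as a covariate would not bias the comparison, but its reliability is in question.
- **The van Elteren fallback** adjusts for the maximum baseline Schiff score and would not use the added covariate. This stands.
- **The models are fixed in Protocol 12.2.6**, so the change is a departure to be recorded, not just a wording edit. This stands.

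A reader might also infer that both Day 56 models rest on a single Day 0 reading. That is not so: the tactile model uses two, the tactile threshold and the Schiff stratum.

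**Conclusion.** The point holds as a low-cost improvement to the Day 56 Schiff model. The range of about 0% to 7% narrower rests on assumed variance shares and correlations. It shrinks to about 0% to 1% in the simulation where response varied between subjects. If Screening adds nothing, the interval is about 0.5% wider.

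A reader might infer that the planned intervals are wider than the collected data allow, or that the planned analysis is wrong. The documents support neither. The first depends on a partial correlation that they do not report, and below about 0.10 the extra covariate would not help. On the second, the planned comparison is unbiased with or without the Screening score.

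The objections reduce the expected gain but do not make the change harmful, provided Screening values are close to complete.

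**What to change.** Before unblinding:

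1. In SAP 4.5.1.1.2, add the Screening Schiff average of the two test teeth as a covariate beside the Day 0 average. Leave the baseline definition and the endpoint as they are.
2. Carry the same covariate to the Schiff analyses at Days 3, 7, 14 and 28 in SAP 4.7.1.2.
3. State in advance how a subject without a Screening value is handled.
4. Record the addition in SAP Section 5, which now reports no changes from the protocol.

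Two further additions are optional: the Screening tactile average in SAP 4.5.1.2.2, and the Baseline tactile average in the Schiff model. The range above covers neither, so it should not be quoted for them.

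The cost is a few sentences and one degree of freedom of 97. No new data are collected.

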4.5.1.1.3 Supportive Analyses

If there is more than 10% difference in the overall number of subjects between the PP and the mITT populations, a PP analysis will be performed for Secondary Efficacy Variable 1 and summarized in [Table 14.2.2.4.2](#).

4.5.1.2 Secondary Efficacy Variable 2

4.5.1.2.1 Secondary Efficacy Endpoint 2 Definition

The second Secondary Efficacy Variable is change from Baseline in tactile threshold (g) at Day 56. Change from Baseline will be derived for the individual teeth first before calculating the average change for the two test teeth.

4.5.1.2.2 Statistical Hypothesis, Model and Method of Analysis

Study product differences will be tested under the null hypothesis:

- H_0 : there is no treatment difference versus the alternate hypothesis;
- H_1 : there is a treatment difference

Change in tactile threshold (g) will be analysed at Day 56 using an ANCOVA model with study product and Baseline Schiff stratification included as factors and Baseline tactile threshold included as a covariate.

Using the above model, adjusted mean change from Baseline, along with 95% CIs will be reported by study product group. P-values testing for non-zero change from Baseline will be presented for both study product groups. Mean difference between study product groups, 95% CIs and p-values will be provided for tactile threshold (g) in [Table 14.2.2.5.1](#). Significance testing will be conducted at the two-sided 5% significance level; no adjustment for multiple comparisons will be made.

The assumption of normality and homogeneity of variance in the ANCOVA model will be investigated, and if violated, an appropriate data transformation or non-parametric method, for example, the van Elteren test, adjusting for the maximum baseline Schiff Sensitivity scores, will be performed.

4.5.1.2.3 Supportive Analyses

If there is more than 10% difference in the overall number of subjects between the PP and the mITT populations, a PP analysis will be performed for Secondary Efficacy Variable 2 and summarized in [Table 14.2.2.5.2](#).

4.5.2 Pharmacokinetic

N/A.

4.6 Analysis of Safety

4.6.1 Adverse Events and Serious Adverse Events

Safety data will be reported for the Safety Population as per study product received. The safety and oral tolerability of the study products will be monitored over the 8-week treatment period by review of reported AEs and incidents. All AEs will be reviewed by the Clinical Research Scientist or Designee prior to database lock and unblinding and will be coded to a system organ class (SOC) and preferred term (PT) using the Medical Dictionary for Regulatory Activities (MedDRA). AEs will be classified as oral or non-oral on the AE page of the eCRF.

Treatment emergent adverse events (TEAEs) are defined as AEs that occur on or after the first study product application at the Baseline visit (if this date is missing a suitable alternative will be used e.g., date of randomization). AEs with an onset date/time prior to the first study product application will be considered as non-treatment emergent.

The following AE tables and listings will be produced, presented by study product group and overall:

- Table of TEAEs by SOC and PT ([Table 14.3.1.1](#))
- Table of TEAEs by Oral/Non-Oral and PT ([Table 14.3.1.2](#))
- Table of treatment-related TEAEs by Oral/Non-Oral and PT ([Table 14.3.1.3](#))
- Table of treatment-emergent treatment-related SAEs by SOC and PT ([Table 14.3.1.4](#)) [only produced if there are more than 5 SAEs]
- Table of treatment-related non-serious TEAEs by SOC and PT ([Table 14.3.1.5](#)) [only produced if there are more than 5 SAEs]
- Listing of all AEs ([Listing 16.2.7.1](#) randomized subjects; [Listing 16.2.7.2](#) non-randomized subjects)
- Listing of deaths ([Listing 14.3.2.1](#))
- Listing of non-fatal SAEs ([Listing 14.3.2.2](#))
- Listing of TEAEs leading to study or treatment withdrawal ([Listing 14.3.2.3](#))

In the event there is nothing to report, a null table or listing will be produced.

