9.3.1 Oral Soft Tissue (OST) Examination

The OST examination will be accomplished by direct observation and palpation, using retraction aids as appropriate, and will include examination of the labial mucosa (including lips), buccal mucosa, and mucogingival folds, gingival mucosa, hard palate, soft palate, tonsillar area, pharyngeal area, tongue, sublingual area, submandibular area

and salivary glands. The results of the examination will be recorded in the CRF as either normal or abnormal with details of any abnormalities. Any abnormality or worsening of a pre-existing condition observed by the clinical examiner or reported by the subject from the OST examination carried out at Screening will be recorded as an AE.

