10 ADVERSE EVENT AND SERIOUS ADVERSE EVENTS

10.1 Definition of an Adverse Event (AE)

An AE is any untoward medical occurrence in a clinical study subject, temporally associated with the use of a study product including any washout or lead-in product (or

medical device), whether or not considered related to the study product, including any washout or lead-in product (or medical device).

NOTE: An AE can therefore be any unfavorable and unintended sign (including an abnormal laboratory finding), symptom, or disease (new or exacerbated) temporally associated with the use of a study product including any washout or lead-in product (or medical device).

Events Meeting the AE Definition:

- Any abnormal laboratory test results (hematology, clinical chemistry, or urinalysis) or other safety assessments (e.g. ECG, radiological scans, vital sign measurements), including those that worsen from baseline, considered clinically significant in the medical and scientific judgment of the investigator (i.e., not related to progression of underlying disease).
- Exacerbation of a chronic or intermittent pre-existing condition including either an increase in frequency and/or intensity of the condition.
- New conditions detected or diagnosed after study product administration even though it may have been present before the start of the study.
- Signs, symptoms, or the clinical sequelae of a suspected drug-drug interaction.
- Signs, symptoms, or the clinical sequelae of a suspected overdose of either study product or a concomitant medication. Overdose per se will not be reported as an AE/SAE unless it is an intentional overdose taken with possible suicidal/self-harming intent. Such overdoses should be reported regardless of sequelae.
- "Lack of efficacy" or "failure of expected pharmacological action" per se will not be reported as an AE. Such instances will be captured in the efficacy assessments. However, the signs, symptoms, and/or clinical sequelae resulting from lack of efficacy will be reported as AE if they fulfill the definition of an AE.

Events NOT meeting the AE definition:

- Any clinically significant abnormal laboratory findings (if applicable) or other abnormal safety assessments which are associated with the underlying disease, unless judged by the investigator to be more severe than expected for the subject's condition.

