10.3 Reporting of Adverse Events

10.3.1 Reporting Period

All AEs, and therefore all SAEs will be collected immediately after a subject consents to participate in the study by the completion (signature) of the ICF and until 5 days following last administration of the study product (or last procedure).

Medical occurrences that began before obtaining informed consent will be recorded in the Medical History/Current Medical Conditions section of the CRF not the AE section.

Details recorded by the subject on a diary or similar document that meet the definition of an AE must also be discussed with the subjects and transcribed in the AE section of the CRF.

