10.6 Follow-up of Adverse Events

After the initial report, the investigator is required to proactively follow up with each subject and provide further information on the subject’s condition.

All AEs (serious and non-serious) will be followed until resolution, until the condition stabilizes, until the event is otherwise explained, or until the subject is lost to follow-up.

The investigator is obligated to perform or arrange for the conduct of supplemental measurements and/or evaluations as may be indicated or as requested by GSK CH to elucidate as fully as possible the nature and/or causality of the AE. This may include additional laboratory tests or investigations, histopathological examinations, or consultation with other health care professionals.

New or updated information will be recorded on the AE CRF page and on the SAE form (subject to the classification of the AE).

The investigator will submit any updated SAE data to GSK CH within 24 hours of receipt of the information.

Investigators are not obliged to actively seek AEs in former subjects. However, if the investigator learns of a SAE, including death, at any time after a subject has been discharged from the study, and considers the event reasonably related to the study product or study participation, the investigator will promptly notify GSK CH by emailing the information to the GSK CH Clinical Operations Safety Reporting email box PPD [REDACTED]. The GSK CH Study Manager or designee will be responsible for forwarding the information to the Case Management Group, Global Clinical Safety and Pharmacovigilance group mailbox at GSK PPD [REDACTED].

The investigator will submit any updated SAE data to GSK CH within the designated reporting time frames.

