12.2.7 Safety Analyses

The Safety population will be used for safety analyses. Safety analyses will be performed according to treatment received. All AEs will be reviewed by the Clinical Research Scientist or Designee prior to database lock and unblinding and will be coded using the MedDRA. During this review stage, AEs will be further categorized as oral or non-oral. AEs will be listed and summarized by treatment received. SAEs will also be listed. AEs will be regarded as treatment emergent if they occur on or after the first treatment application at the Baseline visit. The following AEs tables will be produced, presented by treatment group:

- listing of all AEs (randomized subjects and non-randomized subjects);
- summary of AEs;
- treatment emergent AEs by Oral/Non-Oral and Preferred Term (PT);
- treatment emergent AEs by System Organ Class (SOC) and PT;
- treatment emergent treatment related AEs by Oral/Non-Oral and PT;
- listing of serious AEs (if there are no SAEs, a null listing will be produced; if there are more than 5 treatment emergent serious AEs (SAEs), a table will be produced in place of the listing by SOC and PT);
- non-serious treatment emergent AEs by SOC and PT (only produced if there are more than 5 SAEs);
- listing of incidents (if there are no incidents, a null listing will be produced).

The results of the OST and OHT examinations will be listed and the results of the OST examinations will be tabulated.

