1.3 Treatments

	Acclimatization Dentifrice	Test Dentifrice	Control Dentifrice
Treatment Description	Dentifrice containing 1000 parts per million (ppm) fluoride as sodium monofluorophosphate (SMFP)	Dentifrice containing 5% w/w KNO_3 and 0.454% w/w SnF_2 (1100 ppm fluoride)	Dentifrice containing 0.454% SnF_2 (1100 ppm fluoride)
Product Name	Colgate Cavity Protection (Canadian market)	Experimental dentifrice	Sensodyne Rapid Relief Regular (registered as a Non-prescription Natural Health Product [NNHP] in Canada)

Only the Test and Control dentifrices are considered to be study products.

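### Treatment emergence rests on onset date alone, so an adverse event already open at first use that worsens on study product may be left out of the TEAE tables

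*SAP*

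**What the plan says.** - Protocol 12.2.7 ties treatment emergence to timing: "AEs will be regarded as treatment emergent if they occur on or after the first treatment application at the Baseline visit".
- SAP 4.6.1 repeats this: "Treatment emergent adverse events (TEAEs) are defined as AEs that occur on or after the first study product application at the Baseline visit". It then settles the earlier cases without exception: "AEs with an onset date/time prior to the first study product application will be considered as non-treatment emergent".
- SAP 1.3 places the acclimatization paste outside the definition of study product: "Only the Test and Control dentifrices are considered to be study products".
- Protocol 10.3.1 starts collection well before first use: "All AEs, and therefore all SAEs will be collected immediately after a subject consents to participate in the study". Protocol 10.1 counts events associated with a lead-in product as adverse events.
- On worsening, protocol 10.1 includes among events that meet the AE definition: "Exacerbation of a chronic or intermittent pre-existing condition including either an increase in frequency and/or intensity of the condition".
- On changes to an event already recorded, protocol 10.6 says: "New or updated information will be recorded on the AE CRF page and on the SAE form (subject to the classification of the AE".
- Treatment emergent adverse events are the only safety endpoint in the objectives tables (protocol section 3, SAP 1.2).

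**The concern.** In a dentifrice trial, one tolerability question is whether the product aggravates an oral complaint that the subject already has when first using it. The trial has a lead-in during which such complaints can arise and be recorded. Under a rule based only on onset, an event that opens in the lead-in has a pre-treatment date, and nothing in the TEAE definition lets a later increase in intensity change its status. Take mild mucosal irritation that starts on the acclimatization paste, becomes severe on study product and leads the subject to stop. Depending on how the site enters the change, this either counts as a TEAE or does not. The sole safety endpoint then depends partly on data-entry practice that the plan does not fix.

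**Working it through.** No arithmetic in the plan bears on this, so the check sets the passages side by side.

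**Step 1: can an event be open at first use?** Yes. Collection starts at consent (protocol 10.3.1), acclimatization lasts 2-4 weeks (protocol 4.1), and that paste is not a study product (SAP 1.3).

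**Step 2: does the TEAE rule deal with worsening?** No. The protocol speaks of events that occur from first application. The SAP makes clear that onset decides. Neither adds a criterion for intensity or seriousness.

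**Step 3: does a recording rule deal with it instead?** Not clearly. Protocol 10.6 sends updates to the AE page and does not mention a new record or a new onset date. The exacerbation item in protocol 10.1 could support a new record, but it refers to chronic or intermittent pre-existing conditions. It does not plainly cover an acute event that arose after consent and is already open.

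**Step 4: follow both ways of recording through the displays in SAP 4.6.1 and 4.1.1.**

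| Display | Worsening kept on old record | Worsening entered as new event |
|---|---|---|
| Tables 14.3.1.1 and 14.3.1.2 (TEAEs) | absent | present |
| Table 14.3.1.3 (treatment-related TEAEs) | absent | present if judged related |
| Tables 14.3.1.4 and 14.3.1.5 (produced only with more than 5 SAEs) | absent | present if produced and the event qualifies |
| Listing 14.3.2.3 (TEAEs leading to withdrawal) | absent | present if it led to withdrawal |
| Listing 16.2.7.1 (all AEs, randomized subjects) | present | present |
| Listing 14.3.2.2 (non-fatal SAEs) | present if serious | present if serious |
| Table 14.1.1 and Listing 16.2.1.1 (disposition) | withdrawal counted and listed by reason | same |

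**Step 5: direction.** Let A be the events starting at or after first use, and B those starting earlier that worsen afterwards. When worsening stays on the old record, the current rule counts A, while a rule with a worsening criterion counts A plus B. Since B cannot be negative, the current rule can only give the same count or a lower one.

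**Step 6: scale.** With about 52 subjects per arm (protocol 12.1), one subject whose only qualifying event is in B changes that arm's incidence by 1/52 = 1.9 percentage points. The documents give no figure for how many events are open at first use or how many worsen, so B cannot be estimated from them.

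**The case against.** The strongest reply is that the loss is not written into the text. Protocol 10.6 refers to the AE CRF page without saying that it is the existing entry. Where the protocol does mean the first record, it says so, as for device incidents in 10.9.3. Protocol 10.1 treats exacerbation as an adverse event and does not expressly limit pre-existing to conditions present before consent. CRF completion guidance, which often settles this, is not among the documents. The protocol and SAP definitions agree with each other, the rule is the same in both arms, and the safety analysis is descriptive in an exploratory study. Eligibility is also rechecked at Baseline, which makes a clinically significant oral complaint at first use less likely.

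Most of this stands, and it limits the point to a conditional one. It does not remove the point: if either way of recording is reasonable, the TEAE count is not fully specified.

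Four stronger readings are tempting, and the documents do not support them:
- A reader might infer that every such event drops out of every TEAE table. That requires the old record to be kept, which the text does not settle. Two of the five tables may not be produced at all.
- A reader might infer that the event survives only in the all-AE listing. The non-fatal SAE listing is not restricted to TEAEs, and a withdrawal appears in disposition with its reason.
- A reader might infer that judging soft-tissue findings against Screening ("from the OST examination carried out at Screening will be recorded as an AE") makes the gap worse. An irritation that arose during acclimatization still differs from Screening at later visits, so that reference still flags it.
- A reader might take the length of acclimatization as a measure of the undercount. A share of calendar time says nothing about how many events are open at first use and then worsen.

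**Conclusion.** The point holds in conditional form. The TEAE definition has no worsening criterion, the SAP excludes every earlier-onset event, and the documents do not say how worsening of an open event is recorded. If it is kept on the original record, an event aggravated by study product is missing from the TEAE tables and from Listing 14.3.2.3. The count for the only safety endpoint can be lowered by this, never raised. The number affected is unknown and may be zero; the only scale available is about 1.9 percentage points per omitted subject in an arm of 52. Because both arms follow the same rule, the documents do not show which way a between-arm difference would move. This is a cheap improvement to the specification, not a flaw that undermines the trial.

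**What to change.** In SAP 4.6.1 and protocol 12.2.7, define a TEAE as an event that starts at or after first use of the Test or Control dentifrice, or one that started earlier and then increases in intensity or becomes serious at or after that use. Alongside this, instruct sites to enter such worsening as a new adverse event with its own onset date and causality assessment, so that it reaches the TEAE tables and Listing 14.3.2.3. Protocol 12.2.7 already provides for review of all adverse events before database lock and unblinding, and events open at first use can be checked then.

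The cost is one sentence in each document and one CRF-completion instruction, with no new visits or assessments. The downside is that the reported TEAE count may be slightly higher.
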